## 6.7 PARTICIPANT TRANSFERS

If a participant moves from the area, every effort should be made for the participant to continue on the allocated arm, either by transfer to another site that is taking part in the trial, or by collecting the routine HIV/STI results through a non-participating clinic. In the event of a transfer, an electronic copy of their CRFs should be provided to the new site and the participant will need to sign a new consent form. Once this has been done, the new site will take over responsibility for the participant; until this has been done, responsibility for the participant lies with the original site.

## 6.8 LOSS TO FOLLOW-UP

Participants who fail to attend will be contacted by telephone and/or email, according to the permissions granted at routine clinic registration.

Participants will not be considered lost to follow-up until the trial has ended, unless they have left the UK with no plans to return, and with no means to ascertain HIV status. Efforts will be made

throughout the trial to retain participants, or at the very least to ascertain their HIV status, with particular efforts in relation to annual and final visits.

Interviewers may invite participants who chose to leave the study, to take part in a one to one discussion in order to understand their decision to stop participating in part or all of the study. The standard one to one interview guide would be used in these circumstances as well as the supplementary participant information sheet and consent form.

## 7 SAFETY REPORTING

The principles of ICH GCP require that both investigators and sponsors follow specific procedures when notifying and reporting adverse events or reactions in clinical trials. These procedures are described in this section of the protocol. [Section 7.1 - Definitions](#) lists definitions, [Section 7.3 - Investigator Responsibilities](#) gives details of the investigator responsibilities and [Section 7.4 - MRC CTU Responsibilities](#) provides information on MRC CTU responsibilities.

### 7.1 DEFINITIONS

The definitions of the EU Directive 2001/20/EC Article 2 based on the principles of ICH GCP apply to this trial protocol. These definitions are given in [Table 7.1: Definitions](#).

**TABLE 7.1: DEFINITIONS**

TABLE	DEFINITION
Adverse Event (AE)	Any untoward medical occurrence in a participant or clinical trial subject to whom a medicinal product has been administered including occurrences that are not necessarily caused by or related to that product.
Adverse Reaction (AR)	Any untoward and unintended response to an investigational medicinal product related to any dose administered.
Unexpected Adverse Reaction (UAR)	An adverse reaction, the nature or severity of which is not consistent with the information about the medicinal product in question set out in the Summary of Product Characteristics (SPC) or Investigator Brochure (IB) for that product.
Serious Adverse Event (SAE) or Serious Adverse Reaction (SAR) or Suspected Unexpected Serious Adverse Reaction (SUSAR)	Respectively any adverse event, adverse reaction or unexpected adverse reaction that: 
 
▪ Results in death
 
▪ Is life-threatening*
 
▪ Requires hospitalisation or prolongation of existing hospitalisation**
 
▪ Results in persistent or significant disability or incapacity
 
▪ Consists of a congenital anomaly or birth defect
 
▪ Is another important medical condition***
 

\*The term life-threatening in the definition of a serious event refers to an event in which the participant is at risk of death at the time of the event; it does not refer to an event that hypothetically might cause death if it were more severe, for example, a silent myocardial infarction.

\*\*Hospitalisation is defined as an inpatient admission, regardless of length of stay, even if the hospitalisation is a precautionary measure for continued observation. Hospitalisations for a pre-existing condition (including elective procedures that have not worsened) do not constitute an SAE.

\*\*\* Medical judgement should be exercised in deciding whether an AE or AR is serious in other situations. The following should also be considered serious: important AEs or ARs that are not immediately life-threatening or do not result in death or hospitalisation but may jeopardise the subject or may require intervention to prevent one of the other outcomes listed in the definition above; for example, a medical event that leads to the permanent discontinuation of Truvada; an allergic bronchospasm requiring intensive emergency treatment, seizures or blood dyscrasias that do not result in hospitalisation or development of drug dependency.

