### 6.4 PROCEDURES FOR ASSESSING SAFETY

Participants will be asked one month after starting Truvada and quarterly whether they have had any admissions to hospital, or suffered any significant illnesses that stopped them undertaking their usual daily activities and required medical intervention. A clinical member of the team will determine whether or not an illness that interfered with usual daily activity meets the definitions for Serious Adverse Event (SAE) provided in [Table 7.1: Definitions](#). SAEs should be reported to MRC CTU within 24 hours of the investigator becoming aware of this. Participants will also be asked whether they have had any side-effects sufficient to interrupt or stop their Truvada.

Glomerular filtration rate will be estimated at baseline, and annually. Urinalysis for protein will be assessed at these and interim visits and the presence of 1+ or greater protein that cannot otherwise explained will trigger an additional investigation according to routine clinic practice for patients taking Truvada (either a further creatinine measurement to estimate glomerular filtration rate, or urinary protein:creatinine ratio). In the event that that estimated glomerular filtration rate (eGFR) is less than 50mL/min, or the ratio of protein: creatinine (UPC) greater than 20, the participant will be recalled, their medical history, other medication, dietary supplements and pill taking reviewed, and a repeat test performed in the absence of any protein supplements. If the eGFR is confirmed to be < 50 mL/min or the UPC > 20, then Truvada may need to be interrupted or modified to 4 or less tablets a week pending further investigation and/or referral for specialist opinion. In the event that this leads to discontinuation of Truvada, this meets the definition of 'another important medical condition' as described in [Table 7.1: Definitions](#), and should be reported to MRC CTU within 24 hours of the investigator becoming aware of the event.

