### 7.1.2 EXEMPTED ADVERSE EVENTS

Adverse Events include:

- Any event that leads to the interruption or discontinuation of Truvada, regardless of relationship
- Any event the Investigator considers important to the safety evaluation of Truvada, including bone fractures, renal events and unexplained abdominal pain or headaches
- Overdose of Truvada without signs or symptoms

and any Serious Adverse Event that is:

- An exacerbation of a pre-existing illness
- An increase in frequency or intensity of a pre-existing episodic event or condition
- A condition detected after trial drug administration (even though it may have been present prior to enrolment)
- Continuous persistent disease or a symptom present at baseline that worsens following administration of the study treatment

Adverse Events do not include:

- Medical or surgical procedures; the condition that leads to the procedure is the adverse event
- Pre-existing disease or a condition present before treatment that does not worsen
- Hospitalisations where no untoward or unintended response has occurred, eg, elective cosmetic surgery, social admissions

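### The hospitalisation footnote to Table 7.1 misplaces its worsening qualifier, so admissions for a worsened pre-existing condition can be classed as non-serious, at odds with Section 7.1.2

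*Protocol*

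**What the plan says.** Table 7.1 makes hospitalisation one of six seriousness criteria. Its footnote first defines the term broadly: "Hospitalisation is defined as an inpatient admission, regardless of length of stay, even if the hospitalisation is a precautionary measure for continued observation". It then carves out an exception: "Hospitalisations for a pre-existing condition (including elective procedures that have not worsened) do not constitute an SAE".

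Section 7.1.2, in the same part of the protocol, also deals with pre-existing disease. Among the serious events that count as adverse events it lists "An exacerbation of a pre-existing illness" and "Continuous persistent disease or a symptom present at baseline that worsens following administration of the study treatment". Among the things that are not adverse events it lists "Pre-existing disease or a condition present before treatment that does not worsen" and "Hospitalisations where no untoward or unintended response has occurred, eg, elective cosmetic surgery, social admissions".

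Two places tell sites which text to use when judging seriousness. Section 6.4 reads "A clinical member of the team will determine whether or not an illness that interfered with usual daily activity meets the definitions for Serious Adverse", and the sentence goes on to give Table 7.1 as the source of the SAE definition. Section 7.3.1.A likewise refers the investigator to Table 7.1. Neither cites Section 7.1.2.

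**The concern.** The footnote's qualifier is attached to the wrong noun. A procedure does not worsen; a condition does. With the qualifier inside the bracket, nothing limits the main clause, and it reaches every admission for a condition the participant already had.

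Classification as serious controls what happens next. Section 7.3.1.C asks for a causality assessment of serious events, and an event becomes a serious adverse reaction (SAR) only after that step. Expectedness and SUSAR status follow in 7.3.1.D, and the 24-hour notification in 7.3.1.E applies to SAEs. SARs attributable to Truvada are the first safety outcome in Section 9.2.2. Section 5.2.3 also refers to SAE status in its interruption rule. An admission judged non-serious at the first step enters none of these through the hospitalisation criterion.

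The events are plausible in this population. The exclusion criteria in Section 3.2 do not bar pre-existing illness in general, and Section 5.1 names depression among the common reactions in HIV-positive people taking Truvada in combination therapy. Exposure was also still growing when this version was written, because deferred participants were being offered Truvada early (Sections 1.4 and 6.2.1.C).

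**Working it through.** No figure in the protocol bears on this point, so the check compares the texts.

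**Step 1: what each text excludes.**
- Table 7.1 footnote, literal: admissions for a pre-existing condition, whether or not it has worsened.
- Table 7.1 footnote, with the qualifier moved to the condition: admissions for a pre-existing condition that has not worsened.
- Section 7.1.2: pre-existing disease without worsening, and admissions in which nothing untoward happened.

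The second and third agree. The first does not agree with the third.

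**Step 2: apply them to illustrative records.** These are constructed, not taken from the trial.

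| Admission | Footnote, literal | Footnote, qualifier moved | Section 7.1.2 |
|---|---|---|---|
| A. Elective surgery, condition unchanged | Not an SAE | Not an SAE | Excluded |
| B. Baseline depression worse; no other seriousness criterion met | Not an SAE | SAE | Not excluded; exacerbation is listed |
| C. Baseline renal impairment worse; Truvada permanently stopped for it | SAE by another criterion | SAE | Not excluded |
| D. Pre-existing condition worse and life-threatening | SAE by another criterion | SAE | Not excluded |

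The two readings of the footnote part only at B. In C the event stays serious because Table 7.1 gives as an example "a medical event that leads to the permanent discontinuation of Truvada", and Section 6.4 treats discontinuation after a confirmed renal abnormality in the same way. In D the life-threatening criterion applies.

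**Step 3: does Section 7.1.2 rescue record B?** Not dependably. Its list covers events that are already SAEs, so it presupposes that status and does not confer it. It shows that the authors expected an exacerbation to be capable of being an SAE, which is good evidence of intent. But a site that has applied the literal footnote has already answered no on the hospitalisation criterion.

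**Step 4: do other routes catch record B?** Partly.
- The footnote on other important medical conditions allows medical judgement, but its examples are framed around events without hospitalisation, so an admitted exacerbation fits them awkwardly.
- Section 9.2.2 has a separate outcome for adverse events that lead to interruption or discontinuation of Truvada. Record B appears there if the drug was stopped, even temporarily, but not as an SAR.
- Section 6.4 has sites ask about all hospital admissions, so the admission should be known to the site even if it is not classed as serious.

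**The case against.** The strongest reply is that no clinician would read the footnote literally. Since a procedure cannot worsen, the phrase makes sense only if it refers to the condition, and Section 7.1.2 confirms that meaning. On this view the two sections agree and the remedy is editorial. As a statement of probable intent, that stands: this is most likely a misplaced modifier, and many sites will have read it as intended.

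A reader might infer more than the documents support, in three ways.

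- That the protocol adopts a rule excluding all such admissions and that sites applied it. Sites are directed to Table 7.1, but nothing says that the footnote overrides Section 7.1.2, which lies within the same definitions section, and nothing shows how any site read it.
- That drug-related worsening of existing disease is lost to safety reporting. Only admissions serious through hospitalisation alone are exposed, and some of those still appear under the interruption outcome.
- That a percentage of SARs is missed. The protocol gives no admission rate and no share of admissions due to exacerbation, so any such figure would be an assumption restated as a result. The nearest figure is 7 of 4,500 participants in other trials who had to stop Truvada for toxicity (Section 1.2.1). Applied to the 545 enrolled it gives 545 × 7 / 4,500 ≈ 0.85. That suggests small numbers, but it counts stops for toxicity, not admissions, and cannot size this point.

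The reply does not remove the need to act. The sentence that sites are told to use says, on its face, something different from Section 7.1.2, and a definition of seriousness should not depend on the reader guessing what was meant.

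**Conclusion.** The concern holds as an inconsistency in an operative safety definition. The consequence is a risk of uneven or incomplete classification of SAEs, and hence of SARs, between sites. It is limited to admissions for a worsened pre-existing condition that meet no other seriousness criterion, at sites that take the footnote at its word. Both the number of such admissions and the number of such sites are unknown, so no size can be given. It is probably small.

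Accrual, retention and HIV infection are not touched. SARs belong to the other outcome measures, not the main ones. The point still merits correction because the error runs in one direction, towards under-reporting, and the remedy uses a test that the protocol already contains.

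**What to change.** Reconcile the footnote with Section 7.1.2 by moving the qualifier to the condition. For example: *An admission for a pre-existing condition that has not worsened, including an elective procedure for that condition, is not an SAE.*

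Then ask sites to list any admission already recorded as non-serious on the ground that the condition was pre-existing, and to reassess seriousness and, where it applies, causality under the corrected sentence. Because sites already ask about every admission, the query can be answered from existing records.

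The cost is one sentence in the next amendment and one short data query. Design, sample size and analysis do not change.

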### 7.1.1 MEDICINAL PRODUCTS

The IMP in this study is Truvada.

Adverse reactions include any untoward or unintended response to all drugs. Reactions to an IMP must be reported appropriately.

### 7.1.2 EXEMPTED ADVERSE EVENTS

Adverse Events include:

- Any event that leads to the interruption or discontinuation of Truvada, regardless of relationship
- Any event the Investigator considers important to the safety evaluation of Truvada, including bone fractures, renal events and unexplained abdominal pain or headaches
- Overdose of Truvada without signs or symptoms

and any Serious Adverse Event that is:

- An exacerbation of a pre-existing illness
- An increase in frequency or intensity of a pre-existing episodic event or condition
- A condition detected after trial drug administration (even though it may have been present prior to enrolment)
- Continuous persistent disease or a symptom present at baseline that worsens following administration of the study treatment

Adverse Events do not include:

- Medical or surgical procedures; the condition that leads to the procedure is the adverse event
- Pre-existing disease or a condition present before treatment that does not worsen
- Hospitalisations where no untoward or unintended response has occurred, eg, elective cosmetic surgery, social admissions

### 7.1.3 OTHER STUDY-SPECIFIC REQUIREMENTS

Blood will be collected for creatinine at baseline, and annual follow-up.

Urine will be tested at each clinic visit for the presence of protein according to routine clinic practices. Creatinine will be checked if protein  $\geq 1+$  on dipstick, in order to estimate glomerular filtration rate, or a urine specimen sent for analysis of urinary protein:creatinine ratio ([see Section 6.4](#)).

Weight will be checked at each visit.

## 7.2 OTHER NOTABLE EVENTS

Other notable events include the sexually transmitted infections captured through laboratory screening.

### 7.2.1 PREGNANCY

The trial will only recruit individuals born to the male gender.

## 7.3 INVESTIGATOR RESPONSIBILITIES

SAEs and SARs should be notified to the MRC CTU within 24 hours of the investigator becoming aware of the event.

### 7.3.1 INVESTIGATOR ASSESSMENT

#### 7.3.1.A Seriousness

The investigator should determine at each visit, or telephone contact where this substitutes for a visit, whether or not a Serious Adverse Event has occurred since the previous record, using the definition given in [Table 7.1: Definitions](#).

If the event is serious, then an SAE Form must be completed and the MRC CTU notified within 24 hours.

#### 7.3.1.B Severity or Grading of Serious Adverse Events

The severity of all SAEs and/or SARs in this trial should be graded using the toxicity gradings in **Appendix IV**.

#### 7.3.1.C Causality

The investigator must assess the causality of all serious events or reactions in relation to the trial therapy using the definitions in [Table 7.2: Assigning Type of SAE Through Causality](#). There are five categories: unrelated, unlikely, possible, probable, and definitely related. If the causality assessment is unrelated or unlikely to be related, the event is classified as an SAE. If the causality is assessed as possible, probable or definitely related, then the event is classified as an SAR.

**TABLE 7.2: ASSIGNING TYPE OF SAE THROUGH CAUSALITY**

RELATIONSHIP	DESCRIPTION	SAE TYPE
Unrelated	There is no evidence of any causal relationship	Unrelated SAE
Unlikely	There is little evidence to suggest that there is a causal relationship (for example, the event did not occur within a reasonable time after administration of the trial medication). There is another reasonable explanation for the event (for example, the participant's clinical condition, other concomitant treatment).	Unrelated SAE
Possible	There is some evidence to suggest a causal relationship (for example, because the event occurs within a reasonable time after administration of the trial medication). However, the influence of other factors may have contributed to the event (for example, the participant's clinical condition, other concomitant treatments).	SAR
Probable	There is evidence to suggest a causal relationship and the influence of other factors is unlikely.	SAR

Definitely	There is clear evidence to suggest a causal relationship and other possible contributing factors can be ruled out.	SAR
------------	--	-----

If an SAE is considered to be related to trial treatment and drug is interrupted, refer to [Section 5.2.3 - Dose Modifications, Interruptions & Discontinuations](#).

#### 7.3.1.D Expectedness

If there is at least a possible involvement of the trial treatment, the investigator must assess the expectedness of the event. An unexpected adverse reaction is one not previously reported in the current Summary of Product Characteristics (SPC) or one that is more frequent or more severe than previously reported. The definition of an unexpected adverse reaction (UAR) is given in [Table 7.1: Definitions](#). Please see **Appendix V** for a list of expected toxicities associated with the drug being used in this trial. If a SAR is assessed as being unexpected, it becomes a SUSAR.

#### 7.3.1.E Notification

The MRC CTU should be notified of all SAEs within 24 hours of the investigator becoming aware of the event.

Investigators should notify the MRC CTU of all SAEs occurring from the time of randomisation until 30 days after the last protocol treatment administration. SARs and SUSARs must be notified to the MRC CTU until trial closure. Any subsequent events that may be attributed to treatment should be reported to the MHRA using the yellow card system.

#### 7.3.2 NOTIFICATION PROCEDURE

1. The SAE Form must be completed by the investigator (the consultant named on the Signature List and Delegation of Responsibilities Log who is responsible for the participant's care), with due care being paid to the grading, causality and expectedness of the event as outlined above. In the absence of the responsible investigator, the form should be completed by a member of the site trial team, signed and faxed or emailed as appropriate. The responsible investigator should subsequently check the SAE Form, make changes as appropriate, sign and then re-fax to the MRC CTU or email as soon as possible. The initial report must be followed by detailed, written reports as appropriate.

The minimum criteria required for reporting an SAE are the trial number and date of birth, name of investigator reporting and why the event is considered serious.

2. The SAE Form must be sent by fax to the MRC CTU  
[contact] or email information to **[contact]**
3. Follow-up: participants must be followed up until clinical recovery is complete and laboratory results have returned to normal or baseline, or until the event has stabilised. Follow-up should continue after completion of protocol treatment if necessary. A further SAE Form, indicated as 'Follow-up' should be completed and faxed to the MRC CTU as information becomes available. Extra, annotated information and/or copies of test results may be provided separately. The participant must be identified by trial number, date of birth and initials only. The participant's name should not be used on any correspondence and should be deleted from any test results.
4. Staff should follow their institution's procedure for local notification requirements.

### **SAE REPORTING**

Within 24 hours of becoming aware of an SAE, please fax a completed SAE form to the MRC CTU on:  
[contact] or email information to **[contact]**

## **7.4 MRC CTU RESPONSIBILITIES**

Medically-qualified staff at the MRC CTU and/or a medically-qualified delegate will review all SAE reports received. The causality assessment given by the local investigator at the hospital cannot be overruled; in the case of disagreement, both opinions will be provided in any subsequent reports.

The MRC CTU is undertaking the duties of trial sponsor and is responsible for the reporting of SUSARs and other SARs to the MHRA, research ethics committees and Gilead Sciences, Inc as appropriate. Fatal and life-threatening SUSARs must be reported to the MHRA within 7 days of the MRC CTU becoming aware of the event; other SUSARs must be reported within 15 days.

The MRC CTU will also keep all investigators informed of any safety issues that arise during the course of the trial.

The MRC CTU, as Sponsor, will submit Development Safety Update Reports (DSURs) to the MHRA, Ethics Committees and Gilead Sciences, Inc.

